**Novo Nordisk**

#### 4.4 Study design

This is a prospective, multinational, non-interventional PASS in patients with moderate or severe haemophilia A. Patients fulfilling the inclusion criteria can participate in the study regardless of previous treatment regimen, allowing inclusion of patients previously exposed to N8-GP and/or other FVIII products.

Patients will be treated with commercially available N8-GP according to local clinical practice at the discretion of the physician.

The total study duration is estimated to be 7 years with a planned recruitment period of approximately 2 years. The aim is to collect data on 50 patients on prophylaxis with N8-GP for at least, but not limited to 5 years. Patients may continue in the study for the total planned study duration allowing active data collection for up to 7 years.

#### 4.5 Population

Approximately 60 male haemophilia A patients of any age will be enrolled to allow for completion of 50 patients.

##### Inclusion Criteria:

1. Signed consent obtained before any study-related activities (study-related activities are any procedure related to recording of data according to the protocol).
2. The decision to initiate treatment with commercially available Esperoct® has been made by the patient/Legally Acceptable Representative (LAR) and the treating physician before and independently from the decision to include the patient in this study.
3. Male patients of all ages, according to local label, are allowed in this study
4. Diagnosis of severe or moderate Haemophilia A

##### Exclusion Criteria:

1. Previous participation in this study. Participation is defined as having given informed consent in this study
2. Known or suspected hypersensitivity to N8-GP or related products
3. Mental incapacity, unwillingness or language barriers precluding adequate understanding and cooperation
4. Clinical suspicion or presence of FVIII inhibitors at time of inclusion

#### 4.6 Variables

Data within safety, i.e. number of AEs, will be collected. Data and results from assessments and laboratory analyses performed according to local clinical practice at the participating sites will be recorded upon availability. Consumption of N8-GP will be based on treatment regimen and reported

Protocol  
 NN7088-4029  
 UTN: U1111-1235-6007  
 EU PAS No.

~~CONFIDENTIAL~~

Date: 17 April 2020  
 Version: 2.0  
 Status: Final  
 Page: 14 of 49

**Novo Nordisk**

bleeding episodes and will be reported in the electronic Case Report Form (eCRF) system, based on patients own diary.

#### 4.7 Data sources

Data and results available in the patients' medical records, from assessments and laboratory analyses performed according to local practice at the participating sites and from patients own diary will be recorded in the eCRF.

#### 4.8 Study size

The study is planned to include safety follow-up assessments at routine care visits for at least, but not limited to 5 years with 50 patients. Patients may continue in the study for the total planned study duration allowing active data collection for up to 7 years.

#### 4.9 Data analysis

No formal testing of statistical hypothesis will be performed. All data will be presented using descriptive statistics. Categorical data will be summarized by frequency tables while continuous data will be summarized by mean, standard deviation, median, minimum and maximum value.

#### 4.10 Milestones

First Patient First Visit (FPFV)	03 June 2020
Planned date for Last Patient Last Visit (LPLV)	03 June 2027
Planned completion of non-interventional study report (NSR)	03 May 2028

## 5 Amendments and updates

Amendment or update no	Date	Section of study protocol	Amendment or update	Reason
------------------------	------	---------------------------	---------------------	--------

None

Protocol  
 NN7088-4029  
 UTN: U1111-1235-6007  
 EU PAS No.

~~CONFIDENTIAL~~

Date:  
 Version:  
 Status:  
 Page:

17 April 2020  
 2.0  
 Final  
 15 of 49

**Novo Nordisk**

## 6 Milestones

Milestone	Planned date
Start of data collection	03 June 2020
Defined as First Patient First Visit (FPFV)	
End of study	03 June 2027
Defined as Last Patient Last Visit (LPLV)	
End of data collection	28 August 2027
Defined as Data base Lock (DBL)	
Interim DBL	approximately 2.5 years after FPFV
Registration in the EU PAS Register	Prior to start of data collection, i.e. before FPFV
Final report of study results	03 June 2028
Study progress report	Annual (June 2021-June 2027)

## 7 Rationale and background

Novo Nordisk has developed turoctocog alfa pegol (also referred to as N8-GP), a 40-kDa glycoPEGylated human recombinant coagulation Factor VIII (rFVIII) with an extended half-life, for the prophylaxis and treatment of bleeding episodes in patients with haemophilia A. N8-GP has improved pharmacokinetic (PK) properties including a 1.6 fold increase in terminal half-life compared with standard FVIII products, which offers the possibility of achieving FVIII levels in the range of moderate haemophilia A with a less burdensome every fourth day or twice weekly treatment regimen.

Marketing authorisation applications for Esperoct® have been submitted globally. Esperoct® was approved in the US in February 2019 followed by EU in June 2019, and Canada and Switzerland in July.

The regulatory approval of N8-GP was based on the comprehensive pathfinder™ programme, a phase 1 to 3a clinical programme including 270 unique previously-treated patients (PTPs) children,

Protocol  
NN7088-4029  
UTN: U1111-1235-6007  
EU PAS No.

~~CONFIDENTIAL~~

Date: 17 April 2020  
Version: 2.0  
Status: Final  
Page: 16 of 49

**Novo Nordisk**

adolescents and adults with severe haemophilia A (FVIII activity  $\leq 1\%$ ). The phase 3 trials documented that N8-GP is efficacious for prophylaxis and treatment of bleeding episodes across all age groups and in providing effective haemostasis during and after major surgical procedures. The median annualized bleeding rate for adolescents and adults was 1.18 and for children 1.95. In children, 82 % of their target joints did not bleed during the main phase of the trial, and children overall also showed an enhanced quality of life. The overall success rate for the first treatment of a bleeding episode evaluated within 8 hours was 88 %.

The general safety profile of N8-GP for the treatment of patients with haemophilia A is well examined through the clinical development programme, where N8-GP was well tolerated and has demonstrated a safety profile in the pivotal phase 3 trial in adolescents and adults, in the paediatric phase 3 trial and the surgery phase 3 trial similar to that of currently approved FVIII products.

The Committee for Medicinal Product for Human use (CHMP) has raised a theoretical concern regarding potential long-term effects of PEG accumulation in organs and other tissues. Based on modelling data and supported by analyses of PEG plasma levels in clinical samples from adolescent/adult and paediatric patients participating in the N8-GP phase 3 trials, plasma steady-state PEG concentrations have been reached in the clinical trial programme without any indication of PEG-related adverse effects to date. The clinical safety of long-term exposure to N8-GP – including evaluation of potential clinical consequences of exposure to 40 kDa PEG in organs and tissues – is yet to be established.

As per guideline, it is a request from the European Medicines Agency (EMA) to collect additional clinical data and to ensure consistency between the outcome from the pre-authorisation clinical trials and those from post-approval local clinical practice use of commercially available product. Therefore, a post-marketing investigation should be performed. Novo Nordisk has received an obligation to conduct a Post-Authorisation Safety Study (PASS) to investigate the potential effects of PEG accumulation in organs and other tissues.

The purpose of this non-interventional PASS is thus to gain additional knowledge on the safety of N8-GP in patients with haemophilia A after longer-term treatment and to evaluate possible clinical consequences hereof under observational ('real-world') conditions of local clinical practice.

## **8 Research question and objectives**

### **8.1 Primary objective**

To investigate long-term safety of N8-GP including the PEG moiety of the substance during routine prophylaxis in patients with haemophilia A.

Protocol  
 NN7088-4029  
 UTN: U1111-1235-6007  
 EU PAS No.

~~CONFIDENTIAL~~

Date: 17 April 2020  
 Version: 2.0  
 Status: Final  
 Page: 17 of 49

**Novo Nordisk**

## 8.2 Secondary objective

To further evaluate the general safety including FVIII inhibitors and allergic/hypersensitivity reactions of N8-GP during routine use in patients with haemophilia A under the circumstances for which it was prescribed.

## 8.3 Exploratory objectives

To monitor possible clinical effects of long-term exposure to N8-GP in patients with haemophilia A, including assessments of kidney and liver function parameters, neurologic function and patients' PEG plasma level, besides the number of FVIII treatment requiring bleeding episodes.

# 9 Research methods

In this document physician refers to the individual overall responsible for the conduct of this non-interventional study at the study site. Tasks can be performed by a health care professional according to qualifications and at the discretion of the responsible physician.

## 9.1 Study design

This is a prospective, multi-national, non-interventional post-authorisation study in patients with haemophilia A, prescribed prophylaxis with N8-GP by the treating physician prior to and independent of the decision to include the patient in the study. The study is designed to obtain additional real-life exposure and safety information.

The study is planned to include safety follow-up assessments at routine care visits for at least, but not limited to 5 years with 50 patients. Patients may continue in the study for the total planned study duration allowing active data collection for up to 7 years.

This study aims to observe routine use of N8-GP in any eligible patient in accordance with care prescribed by the treating physician, to the extent that enrolment of patients is allowed under local regulatory rules.

Monitoring of safety will be performed from a patient's first exposure to N8-GP after enrolment in this study defined by completion of informed consent through the patient's last visit in the study (defined as end of study or withdrawal of informed consent). Adverse events (AEs) are expected to be captured through the periodic clinical evaluations every 6-12 months that are routinely undertaken in patients with haemophilia A. Follow-up on any AE will be carried out until resolution of the AE, and if the patient discontinues to the extent allowed by IRB/ethics committees following discontinuation of the study. Exploratory assessment of the patients' PEG plasma level as requested by EMA, will be performed at pre-defined time points (see section [9.2.7.4](#)) and if considered clinically warranted by the responsible physician.

Protocol  
NN7088-4029  
UTN: U1111-1235-6007  
EU PAS No.

CONFIDENTIAL

Date: 17 April 2020  
Version: 2.0  
Status: Final  
Page: 18 of 49

Novo Nordisk

The follow up period after discontinuation of study drug should be as long as possible, preferably until end of study.

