**Figure 9-1 Study Design**

### 9.1.1 Primary endpoint

Endpoint	Time frame	Unit
Number of Adverse Events (AEs) reported during the study period	From inclusion of the patient until end of study	Count of events

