**Novo Nordisk**

### **9.2.7.8 Adverse event, serious adverse events and adverse events of special interest**

All adverse events (AEs), including serious adverse events (SAEs), either observed by the physician or reported by the patient must be recorded and evaluated by the physician. Adverse events of special interest (AESI), which in the evaluation of safety have a special focus, are listed in section [11.1](#) and [appendix A](#).

At each contact with the site during the study, the patient should be asked about AEs since the last contact. Please refer to [appendix A](#) and section [11](#) for AE, SAE and AESI definitions, collection, recording, and reporting times. AE collection and reporting must be performed after signed informed consent and until a patient's last visit in the study.

Bleeding episodes are not considered adverse events unless the bleeding episode is fatal, life threatening or evaluated by the investigator as possibly caused by the study product. Causes to a bleeding episode may be considered as an AE e.g. an injury.

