**Novo Nordisk**

### **9.7.1 Definition of analysis sets**

All safety analyses will be based on the safety analysis set (SAS) where all patients exposed to N8-GP during study period will be included.

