**Novo Nordisk**

All adverse events including all fatal outcomes on N8-GP which occur after informed consent is obtained and until the follow-up visit/end of study visit must be collected and reported to Novo Nordisk.

Adverse events must be reported by the physician on the adverse event form (AE form).

In addition, for serious adverse events and adverse events of special interest (AESIs) further information must be reported by the physician on the safety information form (SIF). A serious AESI should be reported following the same reporting requirements and timelines as for SAEs (see Section 11.2).

The following are defined as AESIs in this study:

1. Allergic reaction including, but not limited to, any acute IgE mediated reaction or delayed type hypersensitivity (clinical signs may include various types of skin rashes) that does not meet the definition of anaphylaxis as described by Sampson et al.
2. Anaphylactic reaction as defined by Sampson et al (as defined in [appendix A](#)).
3. CNS-related adverse events, including but not limited to any learning and behavioural deficits.
4. Thromboembolic events (clinical signs or laboratory indications of arterial and venous thrombosis including myocardial infarction, pulmonary embolism, cerebral infarction/thrombosis, deep vein thrombosis, other clinically significant thromboembolic events and peripheral artery occlusion, see definitions in [appendix A](#)).
5. Medication errors concerning N8-GP. The following should be reported:
  - Administration of wrong drug.
  - Wrong route of administration, such as intramuscular instead of intravenous.
  - Administration of an accidental over- or underdose: The administered dose must deviate from the intended dose to an extent where clinical consequences for the patient were likely to happen as judged by the investigator, although they did not necessarily occur.
6. Renal or hepatic adverse events including new onset of renal or hepatic disorder or impairment.
7. Adverse events of special interest must always be reported to Novo Nordisk. So the AE form and safety information form (SIF) in the eCRF and/or on paper should be filled in.

Protocol  
NN7088-4029  
UTN: U1111-1235-6007  
EU PAS No.

~~CONFIDENTIAL~~

Date: 17 April 2020  
Version: 2.0  
Status: Final  
Page: 36 of 49

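### The primary AE and secondary SAE counts mix time on N8-GP with time after it is stopped, and section 9.1 starts the safety window later than the other sections do

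*Protocol*

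**What the plan says.** All references are to the protocol; no SAP was available.

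- **Objective.** Section 8.1 asks about long-term safety of N8-GP, including its PEG part, in patients on routine prophylaxis.
- **Endpoint window.** Section 9.1.1 sets the time frame of the primary endpoint, a count of AEs, as "From inclusion of the patient until end of study". Section 9.1.2 gives the SAE endpoint the same time frame.
- **After stopping.** Section 9.1 states: "The follow up period after discontinuation of study drug should be as long as possible, preferably until end of study". Section 9.2.5 does not make stopping N8-GP a reason for withdrawal, and section 9.1.4 allows other FVIII products.
- **Analysis set.** Section 9.7.1: "All safety analyses will be based on the safety analysis set (SAS) where all patients exposed to N8-GP during study period will be included". This selects patients, not periods of exposure.
- **Summary.** Sections 9.7.2.1 and 9.7.2.2 plan the number of events over the study period, the number of patients with any event, and listings.
- **Start of the window.** Section 9.1: "Monitoring of safety will be performed from a patient's first exposure to N8-GP after enrolment in this study". Section 9.2.7.8: "AE collection and reporting must be performed after signed informed consent and until a patient's last visit in the study". Section 11.1 covers events "which occur after informed consent is obtained and until the follow-up visit/end of study visit must be collected".
- **PEG.** Sections 9.2.7.4 and 9.7.2.3 plan plasma levels at entry, at two years and at end of study, summarised by visit, with listings and individual profiles.

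**The concern.** The objective is tied to a treatment condition and the endpoint is not. A patient who switches to another FVIII product after a year and stays in follow-up keeps adding AEs and SAEs to the same totals as patients still on N8-GP. Nothing in the planned summary shows how many of the counted events arose in each state. A reader of the final report could not say from the main tables what was seen during prophylaxis. Nor could they see whether anything emerged after stopping, which matters in a study prompted by concern over PEG accumulation.

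The two start points are a smaller, separate inconsistency. Inclusion criterion 2 (section 9.2.2) requires only that the decision to initiate treatment has been made, so a new starter may consent before the first dose. An AE in that gap is inside the window of sections 9.1.1, 9.2.7.8 and 11.1 but before monitoring begins under section 9.1.

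The same mixing affects PEG. The end-of-study visit falls just before the planned last-patient-last-visit date (section 9.2.6.4). A patient who stopped earlier then gives a sample that reflects decline after exposure, and it is averaged with samples from patients still treated.

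**Working it through.** **The plan's own figures.** There is no power or precision calculation to reproduce; section 9.5 says the size follows a regulatory request. The timeline is consistent: 7 years in total minus about 2 years of recruitment leaves 5 years for the last patient. Enrolling 60 so that 50 complete implies 1 − 50/60 = 16.7% non-completion of the *study*. That is not a rate of stopping N8-GP, and the protocol gives no such rate.

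**One patient.** Off-drug share = (F − t)/F, with follow-up F and stopping time t.
- Stop at year 1, followed to year 5: (5 − 1)/5 = 80%.
- Stop at year 1, followed to year 7: (7 − 1)/7 = 86%.

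**The cohort.** If a fraction f stops at time t, and everyone is followed for F years, off-drug share of person-time s = f × (F − t)/F. At mid follow-up (t = F/2) this is f/2 whatever F is. For 60 patients over 5 years there are 60 × 5 = 300 person-years. The values of f are assumed; 16.7% serves only as a reference value.

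| f (assumed) | Stop at 2.5 y: off-drug person-years | Share | Stop at 1 y: off-drug person-years | Share |
|---|---|---|---|---|
| 5% | 7.5 | 2.5% | 12 | 4% |
| 16.7% | 25 | 8.3% | 40 | 13.3% |
| 30% | 45 | 15% | 72 | 24% |
| 50% | 75 | 25% | 120 | 40% |

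**Effect on a pooled rate.** If the AE rate off drug is r times the rate on drug, pooled rate / on-drug rate = 1 − s(1 − r). With r = 0.5 (assumed), the mid-follow-up cases give 1 − 0.025 × 0.5 = 0.99 to 1 − 0.25 × 0.5 = 0.875. The most extreme case in the table gives 1 − 0.40 × 0.5 = 0.80. With r = 1 there is no shift.

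**The start gap.** Share = gap in days / (5 × 365.25).
- Patient already on N8-GP: the background (section 7) mentions dosing twice weekly or every fourth day, so the gap is at most about 3.5 to 4 days, or 0.19% to 0.22% of five years.
- New starter with an assumed gap of 30 to 90 days: 1.64% to 4.93%.

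**Can the periods be separated?** Yes. Section 9.2.8.9 requires the regimen at entry and every change to be recorded with its date. Sections 9.1.4 and 9.2.8.7 require other FVIII products to be documented, preferably with start and stop dates.

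**The case against.** The strongest reply is that follow-up after stopping is intended. The study exists because of a theoretical concern about PEG in organs and tissues (section 7), and a late effect might appear only after the drug is withdrawn. That stands: the quoted sentence in section 9.1 is not an error, and cutting the primary count at the last dose plus some lag would push such events out of the main result. No lag can be derived from the document.

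A reader might infer that off-drug events are being attributed to N8-GP. The document does not support this. Appendix A defines an AE regardless of relatedness and gives each event a causality category, and section 9.7.4 summarises adverse reactions separately. However, a causality judgement on each event does not replace its exposure status, and the primary endpoint is all AEs.

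A reader might also count three different starts of the window. In substance there are two: participation is defined by consent (section 9.2.3, exclusion criterion 1), so inclusion and consent nearly coincide. For patients already on N8-GP the gap is days. Appendix A also frames an AE as occurring in someone using a product, so the status of a new starter's pre-dose event is unclear rather than plainly counted.

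Finally, treatment flags and person-time are often left to a SAP, and their absence here is not the criticism. The criticism is that the protocol itself fixes a window and a pooled count that do not match its objective, and gives conflicting start points.

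**Conclusion.** The point holds in a limited form. Followed as written, the primary and secondary counts include events after N8-GP is stopped, unmarked, while the objective is safety during prophylaxis. Section 9.1 also conflicts with sections 9.1.1, 9.2.7.8 and 11.1 on when the window opens.

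The size cannot be fixed from the document. Under the assumption that 5% to 50% of patients stop at mid follow-up and remain in the study, 2.5% to 25% of person-time is off drug. It would be tempting to turn the 60-to-50 allowance into an annual stopping rate, but patients who leave the study contribute no off-drug time, so that figure does not measure this. Nor is it right that the two kinds of event can never be told apart: the dated records and listings allow it, and only the planned summaries do not.

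No hypothesis is tested, no stated figure is wrong and no data are lost. This is a should-fix, not a must-fix.

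**What to change.** Keep all AE collection, all follow-up after stopping and the overall counts. Then:

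1. Use one start point for the safety window in sections 9.1, 9.1.1 (and 9.1.2), 9.2.7.8 and 11.1.
2. In sections 9.7.2.1 and 9.7.2.2, present AEs and SAEs additionally by period: on N8-GP, after stopping, and before the first dose if there is any such time. Give each period its own person-time, derived from the regimen dates recorded under section 9.2.8.9.
3. In section 9.7.2.3, summarise PEG levels by whether the patient was on or off N8-GP at sampling.

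The cost is wording in a few sections, one derived treatment-period variable and a small number of extra tables. No new data are needed. Settling this before the interim analysis at about 2.5 years (section 9.7.3) would keep interim and final tables comparable.

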**Figure 9-1 Study Design**

### 9.1.1 Primary endpoint

Endpoint	Time frame	Unit
Number of Adverse Events (AEs) reported during the study period	From inclusion of the patient until end of study	Count of events

### 9.1.2 Secondary endpoint

Endpoint	Time frame	Unit
Number of Serious Adverse Events (SAEs) reported during the study period	From inclusion of the patient until end of study	Count of events

